1. BACKGROUND

1.1 Study Disease(s)

Renal cell carcinoma (RCC) & Carbonic Anhydrase IX (CAIX): Renal cell carcinoma (RCC) is the most common neoplasm of the kidney [1], with an estimated 60,000 patients diagnosed annually in the United States [2]. Among cases of RCC, the clear cell subtype (ccRCC) is the most prevalent, accounting for up to 70% of RCCs [3–5]. Common to ccRCC is loss of the Von Hippel-Lindau (*VHL*) tumor suppressor gene [6]. Loss of *VHL* in turn leads to over-expression of carbonic anhydrase IX (CAIX) [7], a membrane-associated enzyme responsible for catalyzing the reversible hydration of carbon dioxide to a bicarbonate anion and a proton [8, 9]. Overexpression of CAIX is known to be presented in approximately 95% of ccRCC tumor specimens [10–12], making it a useful biomarker for this disease.

CAIX has limited expression in normal tissues with the exception of the gastrointestinal tract, gallbladder and pancreatic ducts [8, 9, 13–15]. Feasibility for the non-invasive detection of ccRCC based on CAIX expression has been proved with the radiolabeled antibody G250 [16] and its potential clinical applications has been reviewed previously [17]. However, antibodies as molecular imaging agents suffer from pharmacokinetic limitations, including slow blood and non-target tissue clearance (normally 2–5 days or longer) and non-specific organ uptake. Low molecular weight agents demonstrate faster pharmacokinetics and higher specific signal within clinically convenient times after administration. Low molecular weight agents can also be synthesized in radiolabeled form more easily, and may offer a shorter path to regulatory approval [18].

Targeting CAIX with small molecule inhibitors has proved challenging in part because there exists fifteen human isoforms of carbonic anhydrase. These isoforms share common structural features, including a zinc-containing catalytic site, a central twisted β -sheet surrounded by helical connections, and additional β -strands. The isoforms, however, vary widely in terms of intracellular location, expression levels, and tissue distribution [8, 9]. Significant effort has been expended on the development of sulfonamides and other low molecular weight CAIX ligands for nuclear imaging, but most reported agents have been fraught with low tumor uptake and significant off-target accumulation [19–24].

¹¹¹In-XYIMSR-01. In 2015 Wichert and co-workers identified a promising dual-motif inhibitor of CAIX from a DNA-encoded chemical [25]. We subsequently improved upon this agent by replacing the IRDye750 portion of their molecule with the hydrophilic species 1,4,7,10-tetraazacyclododecane-1,4,7,10-tetraacetic acid (DOTA), which enables convenient radiolabeling with metal isotopes for positron emission tomography (PET), single photon emission computed tomography (SPECT), and radiopharmaceutical therapy [26, 27]. We have termed this agent XYIMSR-01 have previously reported our pre-clinical experience with an indium-111 labeled (¹¹¹In) version of the molecule [27]. SPECT imaging of immunocompromised mice bearing CAIX-expressing SK-RC-52 tumors revealed radiotracer uptake in tumor as early as 1 hour post-injection. Biodistribution studies demonstrated 26% injected dose per gram of radioactivity within tumor at 1 hour. At 24 hours post-injection, Tumor-to- blood, muscle, and kidney, ratios were 178.1 ± 145.4 , 68.4 ± 29.0 and 1.7 ± 1.2 , respectively. Retention of radioactivity was exclusively

observed in tumors by 48 hours, the latest time point evaluated. In total, imaging with ^{111}In -XYIMSR-01 enabled specific detection of ccRCC in this xenograft model, with pharmacokinetics surpassing those of previously described radionuclide-based probes against CAIX.

Dosimetry. Using the biodistribution data generated in the paper by Yang et al. we have estimated the human dosimetry for ^{111}In -XYIMSR-01 agent.

Target Organs	Organ Dose (rem/mCi)	Organ Dose (mSv/MBq)
Adrenals	1.60E-01	4.31E-02
Brain	3.82E-02	1.03E-02
Breasts	6.07E-02	1.64E-02
Gallbladder Wall	1.54E-01	4.15E-02
Lower Large Intestine	1.24E-01	3.36E-02
Small Intestine	1.38E-01	3.73E-02
Stomach Wall	1.47E-01	3.97E-02
Upper Large Intestine	1.21E-01	3.28E-02
Heart Wall	1.38E-01	3.74E-02
Kidneys	4.74E-01	1.28E-01
Liver	1.79E-01	4.84E-02
Lungs	3.43E-01	9.28E-02
Muscle	1.67E-01	4.51E-02
Ovaries	1.39E-01	3.74E-02
Pancreas	1.72E-01	4.65E-02
Red Marrow	1.00E-01	2.71E-02
Osteogenic Cells	1.47E-01	3.98E-02
Skin	6.19E-02	1.67E-02
Spleen	1.59E-01	4.30E-02
Testes	9.07E-02	2.45E-02
Thymus	1.23E-01	3.32E-02
Thyroid	1.14E-01	3.08E-02
Urinary Bladder Wall	1.29E-01	3.49E-02
Uterus	1.35E-01	3.66E-02
Total Body	1.34E-01	3.63E-02

Based on the presented data, we have determined the kidneys to be dose limiting at 0.474 rem/mCi. In accordance with the guidance found in 21 CFR 361.1, 10.55 mCi may be administered to patients in this study.

Toxicology. The toxicology of cold $^{113}/^{115}\text{In}$ -XYIMSR-01 has been studied. Administration of $^{113}/^{115}\text{In}$ -XYIMSR-01 at doses of 11 and 55 $\mu\text{g}/\text{kg}$ was well tolerated by male and female Sprague-Dawley rats. No consistent or treatment-related effects were observed with respect to the following endpoints: survival; clinical signs; body weight; clinical chemistry, hematology,

IRB number: IRB00237314

Version: 3.0 Date: February 22, 2025

and urinalysis parameters; absolute or relative organ weights; or histopathology. These data support the safety of administering ^{111}In -XYIMSR-01 to human subjection.

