2. OBJECTIVES

2.1 Primary Objectives:

The primary objective of this study is to evaluate the safety, tolerability, and feasibility of ^{111}In -XYIMSR-01 SPECT/CT in patients with metastatic ccRCC.

2.2 Secondary Objectives:

- To determine the biodistribution and radiation dosimetry of ^{111}In -XYIMSR-01.
- To characterize the pharmacokinetics of ^{111}In -XYIMSR-01.
- To assess the concordance of findings on ^{111}In -XYIMSR-01 SPECT/CT with conventional imaging.

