4. STUDY PROCEDURES

	Screening/ Baseline ⁹	¹¹¹ In- XYIMSR-01 Dosing and SPECT/CT Imaging	¹¹¹ In-XYIMSR-01 SPECT/CT	Follow-Up visit
	Day-30 to Day 1	Day 1	Day 2, and Day 3 post-injection (24± 1 hour, and 48± 1 hour post-injection)	Within 7 Days from ¹¹¹ In-XYIMSR-01 Administration
Informed Consent & Eligibility	X			
Demographics (date of birth, race, ethnicity)	X			
Medical History	X			
Vital Signs (Blood Pressure, Heart Rate, Temperature) ¹	X	X ¹	X	
Height and weight	X	X	X	
Clinical Labs (Hematology, Chemistry) ²	X	X	X ¹⁰	
Urinalysis	X			
Pregnancy test ³	X	X		
Study Sample Collection ⁴		X		
12-Lead Electrocardiogram (ECG)	X	X ⁵	X ¹¹	
¹¹¹ In-XYIMSR-01 Administration ⁶		X		
SPECT/CT ⁷		X	X	
Adverse Events		X	X	X
Concomitant Medications	X	X	X	X
Standard-of-care Conventional Imaging Review	X			X
Standard-of-care Archived Tumor Tissue or Recent Tumor Biopsy	X			
Follow-Up phone call ⁸				X

¹ On Day 1 Vital Signs (Blood Pressure, Heart Rate, Temperature) will be performed before ¹¹¹In-XYIMSR-01 Administration injection and at the end of ¹¹¹In-XYIMSR-01 SPECT/CT

² Standard of care comprehensive metabolic panel to include measurement of sodium, potassium, chloride, bicarbonate, BUN, creatinine, glucose, total bilirubin, calcium, total protein, albumin, AST, ALT, and alkaline phosphatase.

Standard of care CBC: WBC differential (neutrophils, lymphocytes, monocytes, eosinophils, basophils), WBC count, RBC count, Hematocrit, Hemoglobin, Platelets.

³ For females of childbearing potential, a negative serum or urine pregnancy test will be obtained within a 24-hour period prior to SPECT/CT study.

⁴ Blood samples will be collected at the following time points: pre-dose, 5±2 minutes, 10±2 minutes, 20±5 minutes, 30±5 minutes, 1±0.25 hour, 1.5±0.25 hour, and 24 hours ± 1 hour, post-injection to estimate elimination half-life. About 5 mL of blood will be collected in a heparinized tube at each time point via a peripheral vein.

⁵ A 12-lead electrocardiogram will be performed just prior to ¹¹¹In-XYIMSR-01 administration and immediately following SPECT/CT imaging

⁶ Patients will receive 10.5±1 mCi of radiotracer via an intravenous catheter placed in an antecubital vein or an equivalent venous access.

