⁷ SPECT/CT will be acquired at 2-4, 24± 1 hour, and 48± 1 hour post-injection. For the first three enrolled patients, a total of three fields of view will be acquired and for the remaining 7 patients two fields of view will be acquired. Each SPECT acquisition will be acquired over a 20-30 minute period.

⁸ A safety phone call will also occur 7(±3) days post-dosing. Ongoing adverse events thought to be related to ¹¹¹In-XYIMSR-01 will be followed until resolution of the adverse event, until an alternate cause has been identified, the patient is lost to follow-up, the patient withdraws consent, or it has been determined that ¹¹¹In-XYIMSR-01 is not the cause of the adverse event.

⁹ In order to minimize the need for research-only in-person visits, telemedicine visits may be substituted for in-person research study visits or portions of research study visits where determined to be appropriate and where determined by the investigator not to increase the participants' risks. Prior to initiating telemedicine for study visits the study team will explain to the participant, what a telemedicine visit entails and confirm that the study participant is in agreement and able to proceed with this method. Telemedicine acknowledgement will be obtained in accordance with the Guidance for Use of Telemedicine in Research. In the event telemedicine is not deemed feasible, the study visit will proceed as an in-person visit. Telemedicine visits will be conducted using HIPAA compliant method approved by the Health System and within licensing restrictions.

¹⁰ Safety blood tests: comprehensive metabolic panel to monitor blood chemistries, including kidney and liver function, and blood cell count will be collected at the end of 48 hour SPECT/CT imaging.

¹¹ A 12-lead electrocardiogram will be conducted at the end of 48 hour SPECT/CT imaging.

Pharmacokinetics & Imaging Timepoints:

Procedure	Pre-dose	0 hour	5± 2min.	10± 2 min.	20± 2 min.	30± 5 min.	60± 25 min.	90± 25 min.	2-4 hour	24± 1 hour	48± 1 hour
¹¹¹ In-XYIMSR-01 Administration		X									
Blood & Plasma Collection	X		X	X	X	X	X	X		X	
¹¹¹ In-XYIMSR-01 SPECT/CT Imaging									X	X	X

5. CRITERIA FOR DISCONTINUATION: CANCELLATION/WITHDRAWL PROCEDURES AND EARLY STOPPING RULES.

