5.4 Early Stopping Rules

The safety and tolerability will be assessed on an ongoing basis during the course of the study. The study will be halted and safety and dosing will be further evaluated if any single patient experiences a grade 3-5 toxicity that is believed to be related to radiotracer administration

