6.1.1 Drug Substance

Common Name: ^{111}In -XYIMSR-01

Unit Dose: 10.5 ± 1 mCi of ^{111}In -XYIMSR-01 followed by SPECT/CT imaging

Route of administration: Intravenous catheter placed in an antecubital vein or an equivalent venous access

6.1.2 ^{111}In -XYIMSR-01 Manufacturer

The radiotracer will be manufactured at the Center for Translational Molecular Imaging located

at [name].

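### The permitted activity of 10.5 ± 1 mCi reaches 11.5 mCi, 0.95 mCi above the 10.55 mCi that section 1.1 supports from the kidney dose

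*Combined protocol and SAP*

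**What the plan says.** Under Dosimetry in section 1.1, the sponsor projects human organ doses from preclinical biodistribution data ("we have estimated the human dosimetry for" the tracer). The text after the table states that "we have determined the kidneys to be dose limiting at 0.474 rem/mCi" and then, citing 21 CFR 361.1, that "10.55 mCi may be administered to patients in this study". The organ dose limit behind that figure is not printed.

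The dosing instruction appears in three places, always with the same tolerance:

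- Section 4, footnote 6: "Patients will receive 10.5±1 mCi of radiotracer via an intravenous catheter".
- Section 6.1.1: "Unit Dose: 10.5 ± 1 mCi of" the tracer.
- Section 8.1 repeats 10.5 ± 1 mCi and gives one radiotracer exposure, 1.8 rem, for the whole range.

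Section 5.4, repeated in section 8.1, is the only rule that reopens the dose: "safety and dosing will be further evaluated if any single patient experiences a grade 3-5 toxicity", where the toxicity is thought to be related to the tracer. Section 2.2 makes human dosimetry an objective of this study: "To determine the biodistribution and radiation dosimetry of" the tracer.

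**The concern.** The dosing instruction goes beyond its own stated basis. A dose-limiting organ sets an upper bound, so the activity derived from it reads as a ceiling. The target of 10.5 mCi lies just under 10.55 mCi, but the tolerance of 1 mCi then carries the permitted range well past it. No section caps the activity at 10.55 mCi or justifies more.

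Two consequences follow. An injection of, say, 11.3 mCi is compliant and would not be recorded as a deviation. Nothing in the plan would flag it either, because dosing is re-evaluated on toxicity and not on the activity given. Since human dosimetry is still to be measured, the section 1.1 projection is the only dosimetric support for the dose when patients are injected.

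**Working it through.** **Inputs**

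- Kidney coefficient: 0.474 rem/mCi, or 0.128 mSv/MBq (section 1.1, table and text).
- Supported activity: 10.55 mCi (section 1.1).
- Permitted activity: 10.5 ± 1 mCi (section 4 footnote 6, section 6.1.1, section 8.1).
- Unit conversion: 1 mCi = 37 MBq.

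**Reproducing the plan's figure.** Kidney dose = activity × coefficient.

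- 10.55 × 0.474 = 5.0007 rem, so the implied organ limit is 5 rem.
- In reverse, 5 / 0.474 = 10.549, which rounds to 10.55 mCi.
- The second column agrees: 10.55 × 37 × 0.128 = 49.96 mSv.

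The printed 10.55 mCi is therefore a round organ dose divided by the kidney coefficient. This supports reading it as a maximum.

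**Permitted range**

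| Activity (mCi) | Kidney dose (rem) | Relative to 10.55 mCi |
|---|---|---|
| 10.5 − 1 = 9.5 | 9.5 × 0.474 = 4.50 | −10.0% |
| 10.5 | 10.5 × 0.474 = 4.98 | −0.5% |
| 10.55 | 10.55 × 0.474 = 5.00 | reference |
| 10.5 + 1 = 11.5 | 11.5 × 0.474 = 5.45 | +9.0% |

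**Excess at the upper end**

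- Activity: 11.5 − 10.55 = 0.95 mCi; 0.95 / 10.55 = 9.0%.
- Kidney dose: 0.95 × 0.474 = 0.45 rem.
- Second column: 11.5 × 37 × 0.128 = 54.46 mSv, against 49.96 mSv.

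**Share of the window.** The range is 11.5 − 9.5 = 2.0 mCi wide, and 0.95 / 2.0 = 47.5% of it lies above 10.55 mCi. This describes the allowed range. It does not predict how many injections would fall there.

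For 11.5 mCi to be supported, the organ limit would have to be at least 5.45 rem. The same method would then have given at least 11.5 mCi in section 1.1, not 10.55 mCi.

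**The case against.** The strongest reply is that section 1.1 does not call 10.55 mCi a maximum and prints no organ limit. The 5 rem is a back-calculation, and the documents do not say how the cited regulation treats a dispensing tolerance. On that view 10.55 mCi supports a nominal activity of 10.5 mCi, the tolerance is ordinary practice, and one clarifying sentence would do. This stands in part. The ceiling is an inference, and whether the regulation is breached cannot be settled from the documents. But the nominal reading also leaves a gap, because nothing justifies the activities between 10.55 and 11.5 mCi.

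A second reply is that the effect is small beside the uncertainty of the projection. The 9% arises only at the extreme of the tolerance, and the preclinical data are variable: section 1.1 reports a 24-hour tumor-to-kidney ratio of 1.7 ± 1.2. This is fair as a comment on importance. It does not remove the inconsistency, and an uncertain coefficient is a poor reason to exceed the activity derived from it.

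A third reply is that lowering the target for every patient costs image counts to prevent an excess that is possible only at the top of the range, and that the documents give no image-quality requirement against which to judge 8.5 mCi. This is a real cost of one remedy. A narrower range that keeps the present 9.5 mCi minimum avoids the lower floor.

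**Conclusion.** The concern holds as an inconsistency between sections. No printed calculation is wrong, and the nominal 10.5 mCi (4.98 rem) lies within the supported activity. The tolerance permits up to 0.95 mCi (9.0%) more than section 1.1 supports, with a projected kidney dose 0.45 rem higher.

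The conclusion rests on reading 10.55 mCi as a ceiling and, for the dose in rem, on the preclinical projection of 0.474 rem/mCi. If 10.55 mCi was meant as the basis for a nominal activity, the fault becomes a missing justification for the upper part of the range. The practical effect is modest, and it should be fixed because the dosing rule ought to agree with its own basis.

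**What to change.** Make the same change in section 4 footnote 6, section 6.1.1 and section 8.1, so that the upper end does not exceed 10.55 mCi. The noise figures below assume counts proportional to activity and Poisson noise.

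- **Option A: 9.5 ± 1 mCi** (8.5 to 10.5 mCi; 8.5 × 0.474 = 4.03 to 10.5 × 0.474 = 4.98 rem). This keeps the ±1 mCi tolerance. At nominal activity, counts fall to 9.5 / 10.5 = 0.905 of the present level (9.5% fewer), and relative noise rises by a factor of √(10.5 / 9.5) = 1.051. At the lower end, counts fall to 8.5 / 9.5 = 0.895 and noise rises by √(9.5 / 8.5) = 1.057.
- **Option B: 9.5 to 10.5 mCi, that is 10.0 ± 0.5 mCi** (4.50 to 4.98 rem). This keeps the present minimum. Nominal counts fall to 10.0 / 10.5 = 0.952 and noise rises by √(10.5 / 10.0) = 1.025. The tolerance tightens from 1 / 10.5 = 9.5% to 0.5 / 10.0 = 5%.

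Keeping the 10.5 mCi target and capping at 10.55 mCi would leave only 0.05 mCi of upward room. The documents give no dispensing accuracy, so choose A unless the radiopharmacy can hold ±5%.

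Section 4 footnote 7 allows some compensation: "Each SPECT acquisition will be acquired over a 20-30 minute period". A 20-minute scan recovers nominal counts at 20 × 10.5 / 9.5 = 22.1 minutes (A) or 20 × 10.5 / 10.0 = 21.0 minutes (B). A scan already using 30 minutes cannot, since it would need 33.2 or 31.5 minutes.

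Alternatively, if 10.55 mCi is not a ceiling, state this in section 1.1 and justify activities up to 11.5 mCi (5.45 rem).

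The text change is short, but A and B alter the investigational dose and need an amendment. Neither option settles compliance with the cited regulation, because the documents print no limit and do not say whether the CT dose counts toward it.

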2. OBJECTIVES

2.1 Primary Objectives:

The primary objective of this study is to evaluate the safety, tolerability, and feasibility of ^{111}In -XYIMSR-01 SPECT/CT in patients with metastatic ccRCC.

2.2 Secondary Objectives:

- To determine the biodistribution and radiation dosimetry of ^{111}In -XYIMSR-01.
- To characterize the pharmacokinetics of ^{111}In -XYIMSR-01.
- To assess the concordance of findings on ^{111}In -XYIMSR-01 SPECT/CT with conventional imaging.

3. STUDY DESIGN AND SUBJECT POPULATION

3.1 Study design

The study is phase I, open label, single-arm study designed to evaluate the safety, tolerability, and feasibility of ^{111}In -XYIMSR-01 SPECT/CT in patients with metastatic ccRCC.

3.2 Eligibility Criteria

Inclusion Criteria:

1. Males or female sex
2. ≥ 18 years of age
3. Willingness to provide signed informed consent and comply with all protocol requirements
4. Histological confirmation of RCC with a clear cell component
5. 2-10 sites of disease measuring ≥ 1.5 cm on contrast-enhanced CT and/or MRI imaging of the chest, abdomen and pelvis performed ≤ 60 days prior to the date of study enrollment
6. Screening clinical laboratory values as specified below:
 - Serum bilirubin ≤ 1.5 times the upper limit of normal. For patients with known Gilbert's syndrome, $\leq 3 \times \text{ULN}$ is permitted
 - ALT ≤ 3 times the upper limits of normal
 - AST ≤ 3 times the upper limits of normal
 - Creatinine clearance ≥ 50 mL/min based on Cockcroft-Gault formula
 - Absolute neutrophil count $\geq 1,500 / \text{mm}^3$
 - Platelets $\geq 100,000 / \text{mm}^3$
 - Hemoglobin $\geq 9.0 \text{ g/dL}$
 - White blood cell count $\geq 2,000 / \text{mm}^3$

Exclusion criteria:

- Systemic therapy for the treatment of ccRCC within 12 months of study enrollment.
- Subjects administered any radioisotope within five physical half-lives prior to study drug injection.
- Subjects with any medical condition or other circumstances that, in the opinion of the investigator, compromise obtaining reliable data, achieving study objectives, or completion.
- Women of child-bearing potential (WOCBP) must have a negative serum or urine pregnancy test (minimum sensitivity 25 IU/L or equivalent units of human chorionic gonadotropin) within 24 hours prior to the imaging day.
- Women must not be breastfeeding.

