7.2 Secondary Objectives

Biodistribution and Radiation Dosimetry: A secondary objective of this study is to determine the biodistribution and radiation dosimetry of ^{111}In -XYIMSR-01. To allow for this, SPECT/CT images will be acquired at 2-4, 24 ± 1 hour, and 48 ± 1 hour post-injection. For the first three patients a total of three fields of view will be acquired and for the remaining 7 patients two fields of view will be acquired. Each SPECT acquisition will be acquired over a 20-30 minute period. The first time point acquisition for each field of view will include a high resolution CT. All other time points will be acquired with a low-dose CT.

The acquired PECT/CT images will be used to perform the biodistribution and radiation dosimetry calculations. Time-activity curves (TACs) demonstrating radiotracer activity as a function of time post injection (minutes) will be drawn for the whole body and the following organs: brain, breast, gallbladder, stomach, pancreas, heart wall, lung, liver, bladder, muscle, pancreas, red marrow, spleen, adrenals, upper large intestine, lower large intestine, small intestine, thymus, thyroid, testes and ovaries. Individual organ residence times will be calculated by fitting an exponential function to the TAC data and analytically integrating the fitted functions from zero to infinity. Organ specific mean radiation-absorbed dose estimates for ^{111}In -XYIMSR-01 will be calculated from the individual organ residence times. Reference organ mass values will be adjusted based on actual organ masses. The OLINDA software package will be used to determine the absorbed dose [28].

Characterization of Pharmacokinetics: The pharmacokinetic profile of ^{111}In -XYIMSR-01 will be determined as a secondary endpoint of the study. ~5 mL of blood will be collected in heparinized tubes at pre-dose, 5 ± 2 minutes, 10 ± 2 minutes, 20 ± 5 minutes, 30 ± 5 minutes, 1 ± 0.25 hour, 1.5 ± 0.25 hour, and 24 hours ± 1 hour, post-injection to estimate elimination half-life. The collected blood will be evaluated for total radioractivity, the ratio of free versus protein-bound radiotracer, and measurement of the relative percentage of radiotracer and its metabolites.

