Comparison with Anatomical Imaging: As an initial assessment of the diagnostic performance of ^{111}In -XYIMSR-01 SPECT/CT, findings on this novel imaging test will be compared to those on conventional imaging (CT and/or MRI). Using descriptive statistics we plan to summarize the number of lesions that are detected with all imaging modalities, the number of lesions detected

with ^{111}In -XYIMSR-01 SPECT/CT but not with conventional imaging, and the number of lesions detected with conventional imaging but not by ^{111}In -XYIMSR-01 SPECT/CT.

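### The conventional scan may be 60 to about 90 days older than the SPECT/CT, and section 7.2 does not separate lesions new since that scan from SPECT-only detections

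*Combined protocol and SAP*

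**What the plan says.** Section 2.2 lists the comparison as a secondary objective: "To assess the concordance of findings on ^{111}In -XYIMSR-01 SPECT/CT with conventional imaging". In section 7.2, under the comparison with anatomical imaging, descriptive statistics are planned for three lesion counts: seen on all modalities, detected "with ^{111}In -XYIMSR-01 SPECT/CT but not with conventional imaging", and the reverse. The comparator is described only as CT and/or MRI. No particular scan is named, no maximum interval is set, and nothing is said about lesions that arise between the two examinations.

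The only timing rule for the conventional scan is inclusion criterion 5 in section 3.2, which requires contrast-enhanced CT and/or MRI "performed ≤ 60 days prior to the date of study enrollment". The study calendar in section 4 places consent, eligibility and the other screening items between Day -30 and Day 1, with injection on Day 1. The date of enrollment within that window is not defined. The calendar also marks "Standard-of-care Conventional Imaging Review" at screening and again at the follow-up visit.

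Two further provisions bear on the point. Section 3.2 excludes "Systemic therapy for the treatment of ccRCC within 12 months of study enrollment". Section 7.2, under dosimetry, states: "The first time point acquisition for each field of view will include a high resolution CT". A footnote to the section 4 calendar gives the sessions: "SPECT/CT will be acquired at 2-4, 24± 1 hour, and 48± 1 hour post-injection".

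**The concern.** The three counts are meant to give a first look at diagnostic performance. A lesion in the SPECT-only count will naturally be read as one that the tracer showed and anatomical imaging did not. That reading assumes that both examinations looked at the same disease state.

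Here they may be up to about three months apart, in patients with metastatic disease who had no systemic therapy in the 12 months before enrollment. A lesion that was absent or too small to see on the conventional scan, and is present at injection, falls into the SPECT-only count for a reason unrelated to the tracer's sensitivity. With 10 patients and raw lesion counts, a few such lesions could change the impression the table gives, and no later modelling step would correct it.

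**Working it through.** The plan states no scan-to-injection interval, so there is no figure of its own to reproduce. The permitted interval follows from date arithmetic.

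**Inputs**
- Maximum age of the conventional scan at enrollment: 60 days (section 3.2).
- Screening window: Day -30 to Day 1, with injection on Day 1 (section 4). From Day -30 to Day 1 is 30 days if there is no Day 0, and 31 if there is.
- Last SPECT/CT: 48 hours after injection, or 2 days (section 4).

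**Formula**

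Maximum interval to injection = 60 + (days from enrollment to Day 1). Add 2 for the 48-hour session.

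| Enrollment dated at | Maximum to injection | Maximum to 48-hour SPECT/CT |
|---|---|---|
| Day 1 | 60 + 0 = 60 days | 62 days |
| Day -14 (illustrative) | 60 + 14 = 74 days (75 with a Day 0) | 76 (77) days |
| Day -30 | 60 + 30 = 90 days (91 with a Day 0) | 92 (93) days |

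These are upper limits for each choice of enrollment date. A patient with a recent scan has a shorter interval.

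**How the section 7.2 counts treat each kind of lesion seen on SPECT/CT**

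1. Visible on the conventional scan: counted as seen on both.
2. Present at the conventional scan, not shown by it, and not changed since: counted as SPECT-only. This is added detection by the tracer.
3. Arose, or grew enough to become visible, after the conventional scan: also counted as SPECT-only. This may be elapsed time alone.

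The count as written cannot tell 2 from 3.

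**Does anything else in the plan separate them?**

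- The imaging review at follow-up is a review of standard-of-care imaging. It requires no new scan, and section 7.2 does not refer to it. If a newer scan happens to exist, nothing says that it becomes the comparator.
- The CT at the first SPECT/CT session is acquired 2 to 4 hours after injection, so it shows anatomy on the day of the tracer. If the same fields are imaged at each session, any SPECT-only lesion lies in a field that this CT covers. It could therefore help to separate 2 from 3, but section 7.2 mentions it only for dosimetry and does not use it in the comparison.

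**The case against.** The strongest reply is that this is a small first-stage safety study. The comparison is secondary, descriptive and untested, and no claim that the tracer finds more disease is planned. An interval of about 90 days needs both the oldest permitted scan and enrollment at Day -30. A second imaging review is already in the calendar. All of this is right and keeps the point minor. It does not remove it: even 60 days is not dealt with in the analysis, and two review points with no named comparator leave the choice of scan to be made after the images have been seen.

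Three stronger readings are tempting, and the documents do not support them.

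- A reader might infer that the SPECT-only count is definitely biased upward. The text supports only that it can be inflated. No growth rate is given. Moreover, only prior systemic therapy is excluded; local treatment of a lesion between the scans is not, and it could raise the conventional-only count instead.
- A reader might try to size the effect by assuming a tumor doubling time and asking which lesions would reach 1.5 cm by the day of SPECT/CT. But 1.5 cm is the eligibility size for disease sites in section 3.2, not a detection limit. A smaller lesion already visible on the older scan would count as seen on both and never enter the SPECT-only count. The documents give no detection limit for either modality, so such a calculation does not measure this bias.
- A reader might infer that the first-session CT settles the matter. Section 3.2 requires contrast for the conventional imaging; section 7.2 does not say that the SPECT/CT's CT is contrast-enhanced. A lesion visible on it is informative. A lesion not visible on it is only weak evidence that the tracer alone detected it.

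**Conclusion.** The point holds as a minor one. The comparator scan may be 60 to about 90 days older than the injection, depending on when enrollment is dated. Section 7.2 neither names that scan nor separates lesions that appeared or grew in the interval, so the SPECT-only count can be inflated. How far cannot be computed from the documents.

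The conclusion rests on the literal wording of the three counts and on the absence of any limit counted to injection. It also assumes that the scan used for eligibility may serve as the comparator, which the plan allows but does not state. The primary safety objective and the sample size are not affected.

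**What to change.** Change the wording of the anatomical comparison in section 7.2:

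1. Name as comparator the available conventional scan closest to injection, including any found at the follow-up imaging review.
2. Tabulate, by patient, the days from that scan to injection.
3. Check each SPECT-only lesion on the high-resolution CT from the first SPECT/CT session and report two groups: (a) visible on that CT but absent on the conventional scan, labelled as possible interval change; (b) visible on neither, labelled as having no anatomical correlate, with the caveat that the CT is not stated to be contrast-enhanced.

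This uses images the plan already acquires and adds no patients, visits or radiation. The cost is a small amount of extra image review, and fewer lesions will be labelled tracer-only. The eligibility window does not need to change for this.
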